6.3 Protocol Therapy Discontinuation

The reason for discontinuation of protocol therapy will be documented on the electronic case report form (eCRF).

Instructions for management and discontinuation of therapy for common or expected AEs is included in sections 17.1 and 17.2. Please refer to these sections for instructions regarding therapy discontinuation for diarrhea/colitis, hepatic toxicity, renal toxicity, pulmonary toxicity, endocrinopathy toxicity, skin toxicity, neurologic toxicity, periorbital edema, uveitis, and CK or LDH elevation. In addition, criteria for discontinuation due to hematologic toxicity are outlined in section 6.1. In addition to these, a subject will also be discontinued from protocol therapy and followed up per protocol under the circumstances outlined below.

- Documented disease progression
- The treating physician thinks a change of therapy would be in the best interest of the subject
- The subject requests to discontinue protocol therapy, whether due to unacceptable toxicity or for other reasons
 - If a subject decides to prematurely discontinue protocol therapy (“refuses treatment”), the subject should be asked if he or she may still be contacted for further scheduled study assessments. The outcome of that discussion should be documented in both the medical records and in the eCRF.
- A female subject becomes pregnant
- Any Grade 3 or higher infusion-related reactions and hypersensitivity requiring discontinuation. Any re-initiation of therapy in this circumstance would require consultation with the Sponsor’s Medical Monitor or designee.
- Isolated Grade 3 electrolyte imbalances/abnormalities that are not associated with clinical sequelae
- Any Grade 4 drug-related AE or laboratory abnormality not addressed in sections 6.1, 17.1, or 17.2, except for the following events which do not require discontinuation:
 - Refractory hematologic toxicities as in section 6.1
 - Isolated Grade 4 amylase or lipase abnormalities that are not associated with symptoms or clinical manifestations of pancreatitis. The Sponsor’s Medical Monitor or designee should be consulted for Grade 4 amylase or lipase abnormalities.
 - Isolated Grade 4 electrolyte imbalances/abnormalities that are not associated with clinical sequelae and are corrected with supplementation/appropriate management within 72 hours of their onset
 - Grade 4 drug-related endocrinopathy AEs, such as adrenal insufficiency, adrenocorticotrophic hormone deficiency, hyper- or hypothyroidism, or glucose intolerance, which resolve or are adequately controlled with physiologic hormone replacement (corticosteroids, thyroid hormones) or glucose-controlling agents, respectively, may not require discontinuation after discussion with and approval from the Sponsor’s Medical Monitor or designee.
- If CK is elevated, CK subsets, EKG and troponin will be obtained as outlined in section 17.2. If troponin is elevated above institutional upper limit of normal, evaluation of EF will be performed.

- If Grade ≥ 2 myocarditis is confirmed per AHA diagnostic criteria (Bozkurt, Circulation. 2016 Dec 6;134(23):e579-e646.), patient will be taken off protocol.
- Any event that leads to delay in dosing lasting > 6 weeks from the previous dose requires discontinuation, with the following exceptions:
 - Therapy discontinuation due to achievement of a CR as outlined in Section 5
 - Dosing delays to manage drug-related AEs are allowed. Prior to re-initiating treatment in a participant with a dosing delay lasting > 6 weeks from the previous dose, the Sponsor's Medical Monitor or designee must be consulted. Tumor assessments should continue as per-protocol even if dosing is delayed. Periodic study visits to assess safety and laboratory studies should also continue per protocol, or more frequently if clinically indicated during such dosing delays or per the Investigator's discretion.
 - Dosing delays lasting > 6 weeks from the previous dose that occur for non-drug-related reasons may be allowed if approved by the Sponsor's Medical Monitor or designee. Prior to re-initiating treatment in a participant with a dosing delay lasting > 6 weeks, the Sponsor's Medical Monitor must be consulted. Tumor assessments should continue per protocol even if dosing is delayed. Periodic study visits to assess safety and laboratory studies should also continue per-protocol or more frequently if clinically indicated during such dosing delays or per the investigator's discretion.
- Any AE, laboratory abnormality, or intercurrent illness which, in the opinion of the investigator, presents a substantial clinical risk to the participant with continued cabiralizumab and/or nivolumab dosing
- If the causality of the AE requiring discontinuation is confirmed to be due to one of the study drugs in the combination therapy, the other drug(s) may be continued per-protocol schedule under the following scenarios:
 - Timely resolution of the AE based on the treatment modification table
 - Clinical benefit is shown by the participant based on investigator assessment.

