7. STUDY CALENDAR & EVALUATIONS

	Screen	Cycle Number ²					6 months post CR ¹⁰ / observation	Safety follow up 30 days ^{2,3} post last dose	Long-term Follow up ⁴ Every 3 months (±14 days)
	-28 days	1	2	3	4	5+			
		D1 ¹	D1	D1	D1	D1			
Cycle= 14 days									
REQUIRED ASSESSMENTS									
Review of eligibility criteria, Informed Consent	X								
Medical History ¹⁶ , Diagnosis and Staging (Lugano ⁵)	X								
Physical Exam, Vital Signs ⁶ , ECOG PS ⁷	X	X	X	X	X	X ¹⁷	Q3 mos	X	
EKG	X								
AEs & Concomitant Medications	X	X	X	X	X	X		D30, 100 ³	X ³
LABORATORY ASSESSMENTS									
Complete blood cell count with differential (CBC) ¹⁵	X	X	X	X	X	X	Q3 mos	X	
Comprehensive metabolic profile (CMP) ^{8, 15}	X	X	X	X	X	X	Q3 mos	X	
Mineral panel (phosphorus, magnesium, calcium) ¹⁵	X	X	X	X	X	X	Q3 mos	X	
Creatine kinase, LDH ¹⁵	X	X	X	X	X	X	Q3 mos	X	
Amylase, lipase ¹⁵	X	X	X	X	X	X	Q3 mos	X	
TSH, free T4, cortisol ¹⁵	X	X		X		C5, 7, etc	Q3 mos	X	
Pregnancy test (serum or urine) in WOCBP ⁹	X	X		X		C5, 7, etc ⁹			
DISEASE ASSESSMENT									
PET/CT Scan ¹⁰	-30d					X ¹⁰	Q6 mos		
Bone marrow aspirate and biopsy (unilateral) ¹¹	X					X	X ¹¹		
TREATMENT EXPOSURE									
Nivolumab 240 mg IV		X	X	X	X	X			
Cabiralizumab 4 mg/kg IV		X	X	X	X	X			
CORRELATIVE STUDIES (SPECIMEN COLLECTION)									
Fresh tumor tissue biopsy ¹²	X					C5 ¹³ , @PR ¹³			
Whole blood for somatic baseline		X							
PBMCs and plasma ¹⁴		X		X		C5,@imaging	@imaging	X	
BANKING SAMPLES (SPECIMEN COLLECTION)									
Whole Blood ¹⁴		X		X		C5, @imaging	@imaging	X	
Serum		X		X		C5, @imaging	@imaging	X	
Tumor Tissue ¹²	X					C5 ¹³ , @PR ¹³			
FOLLOW-UP									
Disease progression									X

Key to Footnotes

¹If screening (baseline) labs were performed within 7 days of C1D1 of treatment, these do not need to be repeated.

²A window of 3 days will be applied to all treatment study visits; for safety follow-up visit, tumor imaging, bone marrow biopsy, and lymph node biopsy, a 7-day window will apply.

³A safety follow-up visit will occur 30 days (± 7 days) after the last dose of treatment. Subjects who have an ongoing \geq grade 2 or serious AE (SAE) at this visit will continue to be followed until the AE resolves to \leq Grade 1 or baseline, is deemed clinically insignificant, and/or until a new anti-cancer treatment starts, whichever is earlier. AEs will be collected for 100 days (± 14 days) after the end of treatment. See Section 11.2.

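### Section 6.3 stops therapy for an isolated Grade 3 electrolyte abnormality without sequelae, yet exempts the same abnormality at Grade 4 if it is corrected within 72 hours

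*Combined protocol and SAP*

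**What the plan says.** Section 6.3 first refers to Sections 17.1 and 17.2 for discontinuation rules on expected toxicities and to Section 6.1 for hematologic toxicity. It then introduces a further list: "In addition to these, a subject will also be discontinued from protocol therapy and followed up per protocol under the circumstances outlined below".

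Three items in that list matter here.

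- Grade 3 item, standing alone: "Isolated Grade 3 electrolyte imbalances/abnormalities that are not associated with clinical sequelae".
- Grade 4 item, immediately after it: "Any Grade 4 drug-related AE or laboratory abnormality not addressed in sections 6.1, 17.1, or 17.2". This item has its own sub-list of events that do not require discontinuation. One of them is "Isolated Grade 4 electrolyte imbalances/abnormalities that are not associated with clinical sequelae and are corrected with supplementation/appropriate management within 72 hours", counted from onset.
- Investigator-judgment item, near the end: "Any AE, laboratory abnormality, or intercurrent illness which, in the opinion of the investigator, presents a substantial clinical risk to the participant" if dosing continues.

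The study calendar in Section 7 schedules a mineral panel (phosphorus, magnesium, calcium) and a metabolic profile (including sodium, potassium and chloride) on Day 1 of each 14-day cycle.

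**The concern.** A discontinuation rule should be at least as strict for the more severe grade as for the less severe one. Here the order is reversed. A patient with a Grade 3 electrolyte value and no clinical consequence comes off therapy. A patient with the Grade 4 value, also without consequence, stays on if it is corrected in time.

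This is an operative treatment rule and not background text, and the calendar tests it at every cycle. At stake is treatment exposure in a relapsed or refractory population of at most 33 patients. Someone who might still respond could be taken off both drugs for a finding that supplementation would correct. A site that sensibly kept the patient on treatment would be departing from the written protocol.

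**Working it through.** The point is textual and the plan gives no figure to reproduce. The check sets the rules side by side, looks for anything that resolves them, and then asks whether any statistical quantity depends on them.

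**Step 1. What Section 6.3 requires for an electrolyte abnormality.**

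| Event | Result under 6.3 as written |
|---|---|
| Grade 3, isolated, no sequelae, any cause, corrected or not | Discontinue |
| Grade 3 with sequelae | Not listed; investigator or treating-physician judgment |
| Grade 4, drug-related, isolated, no sequelae, corrected within 72 hours | Exempt |
| Grade 4, drug-related, with sequelae or not corrected in time | Discontinue |
| Grade 4, not drug-related | Outside the Grade 4 item; judgment only |

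Rows 1 and 3 show the inversion. The Grade 3 item is stricter in two further respects: it is not limited to drug-related events, and it has no correction window.

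**Step 2. Whether another section resolves it.** Section 6.1 covers hematologic toxicity. Section 17.1 covers gastrointestinal, hepatic, renal, pulmonary, endocrine, skin, neurologic, periorbital and uveitis events. Section 17.2 covers CK and LDH. None sets an electrolyte rule.

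**Step 3. Whether the rule fits the rest of the protocol.** Several Grade 3 findings lead to a delay with the option to resume:

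- hematologic toxicity that improves to below Grade 3 (6.1);
- diarrhea or colitis that settles within 28 days (17.1.1);
- creatinine that returns to Grade 1 or baseline before the next dosing visit (17.1.4).

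For CK above 10 times the upper limit of normal with normal isoenzymes, dosing continues (17.2). Some Grade 3 toxicities do end therapy at once, such as pneumonitis and neurologic events, but there Grade 4 is treated the same way. Nowhere else is Grade 3 handled more strictly than Grade 4.

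**Step 4. Whether lost formatting explains it.** The Grade 3 item comes before the Grade 4 item and its exception clause. Restoring a lost indent would place it under the preceding item, on infusion reactions, which has no exception list.

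**Step 5. Whether the design figures depend on it.** Section 12.3 stops enrollment at the interim analysis in three cases: 7 or more patients with any Grade 4 event, 3 or more with a Grade 4 event requiring discontinuation under Section 6.3, or any drug-attributable Grade 5 event. A Grade 3 event enters none of these counts. The simulations take the complete response rate, overall response rate and Grade 4+ event rate as inputs, so the Grade 3 item is not an input either.

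**The case against.** The strongest reply is that the list in Section 6.3 is not purely a list of triggers. One item is a work-up instruction for raised CK. Another, beginning "If the causality of the AE requiring discontinuation is confirmed to be due to one of the study drugs in the combination therapy", is a permission to continue the other drug. On that view the electrolyte line is plainly a misplaced exception that no sensible site would apply literally. The part about intent is plausible: the line does read like an exception that lost its place. But the CK and causality items carry their own instructions, whereas the electrolyte line carries none, so the lead-in supplies one, namely discontinue. The permission to continue the other drug needs causality confirmed to one study drug, so it gives no relief for an electrolyte value unrelated to treatment.

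A second reply is that Grade 3 with sequelae, though unlisted, is not left without protection, because the judgment criteria cover it. That stands. The defect is over-stopping, not a safety gap.

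A third reply is that patients who discontinue are still followed per protocol, and that no error rate, power figure or endpoint definition is shown to change. That also stands, and it limits the point to a correction of wording.

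**Conclusion.** The defect is real: as written, the milder electrolyte abnormality has the stricter discontinuation rule. The conclusion rests on reading the lead-in as governing any listed item that has no instruction of its own. That the line is a drafting slip is inference; that it currently acts as a trigger is the text.

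The consequence is possible needless loss of therapy for individual patients. It cannot be sized, because the documents give no rate of isolated Grade 3 electrolyte abnormalities.

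Three stronger readings are tempting and are not supported.

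- A reader might infer that a given number of the 33 patients would be lost, or that power falls by some amount. Any such figure would rest on an invented rate.
- A reader might infer that the interim safety rule is distorted because it cites Section 6.3. It counts Grade 4 discontinuations only, so the Grade 3 item does not reach it.
- A reader might add that the neighboring exception, "Refractory hematologic toxicities as in section 6.1", contradicts Section 6.1, which ends therapy when such toxicity fails to improve. The Grade 4 item already leaves out events addressed in 6.1, and 6.3 sends hematologic discontinuation there. The exception therefore has no operative effect and does not widen this point.

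**What to change.** Delete the Grade 3 electrolyte item from Section 6.3. If the sponsor prefers to keep a statement, put it in a separate sentence saying that isolated Grade 3 electrolyte abnormalities without sequelae do not require discontinuation. Do not simply move the line under the Grade 4 exceptions: that sub-list qualifies a Grade 4 rule, so a Grade 3 entry there would have no effect.

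No protection is lost. A Grade 3 electrolyte event that the investigator considers a substantial clinical risk still leads to discontinuation under the existing judgment criterion.

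The cost is a one-line wording amendment. It needs no new visits, tests, patients or statistical rework.

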6.1 Dose Delays/Dose Modifications

Guidelines for delaying, restarting, or discontinuing therapy for various toxicities is included in sections 17.1 and 17.2. Dose modifications are not permitted for this protocol, except if Day 1 weight change by >10% necessitates a change in the dosing of cabiralizumab. If therapy is delayed, then next infusion date will be considered day 1 of the subsequent cycle.

In addition to sections 17.1 and 17.2, please see below for dose delays related to hematologic toxicity:

- For Grade 1-2 (neutrophils <LLN to 1,000/ μ L, hemoglobin <LLN to 8 g/dL, platelets <LLN to 50,000/ μ L)
 - Rule out alternative causes
 - Continue cabiralizumab and nivolumab therapy
 - Monitor CBC per schedule of events
 - If worsens, treat as grade 3-4 toxicity
- For Grade 3-4 (neutrophils < 1,000/ μ L, hemoglobin < 8 g/dL, platelets < 50,000/ μ L)
 - Rule out alternative causes
 - Delay cabiralizumab and nivolumab therapy. If the AE requiring dose delay was due to one of the study drugs, the non-offending drug may be continued, taking into account the safety and clinical benefit to the patient.
 - Treat autoimmune cytopenias per standard institutional guidelines (examples below):
 - Immune thrombocytopenia may be treated with steroids, immune globulin, or rituximab
 - Immune mediated hemolytic anemia may be treated with steroids, immune globulin, or rituximab
 - Immune mediated neutropenia may be treated with steroids, colony stimulating factors, or immune globulin
 - If improves to < grade 3:

- May resume cabiralizumab and nivolumab therapy per protocol
- If does not improve or worsens:
 - Discontinue therapy. If the AE requiring discontinuation was due to one of the study drugs, the non-offending drug may be continued, if there is timely resolution of AE and clinical benefit is shown by patient.
 - Continue to treat immune mediated cytopenias per standard algorithms
 - Continue follow up until resolution
- Grade 3 drug-related thrombocytopenia associated with grade ≥ 2 bleeding requires discontinuation regardless of duration of thrombocytopenia.

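### Section 6.3 exempts refractory hematologic toxicity from discontinuation although section 6.1, which it names as the source of those criteria, requires it; stopping rule 2 counts by section 6.3

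*Combined protocol and SAP*

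**What the plan says.** Section 6.1 covers Grade 3-4 neutropenia, anemia and thrombocytopenia. Both drugs are delayed, and they may resume once the toxicity is below Grade 3. For the other branch, "If does not improve or worsens", the instruction is: "Discontinue therapy. If the AE requiring discontinuation was due to one of the study drugs, the non-offending drug may be continued", subject to timely resolution and clinical benefit.

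Section 6.3 opens by saying that "criteria for discontinuation due to hematologic toxicity are outlined in section 6.1". It then adds further reasons to stop therapy. One is "Any Grade 4 drug-related AE or laboratory abnormality not addressed in sections 6.1, 17.1, or 17.2", qualified by "except for the following events which do not require discontinuation". The first event in that exception list is "Refractory hematologic toxicities as in section 6.1".

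Section 12.3 sets three toxicity rules for the first 17 subjects. Rule 1 stops enrollment at 7 or more subjects with any Grade 4 AE. Rule 2 stops it at 3 or more subjects whose Grade 4 AE requires discontinuation of study treatment, and it identifies those events by reference to section 6.3. Rule 3 concerns drug-attributable Grade 5 AEs.

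**The concern.** Section 6.1 does not use the word refractory. Its only branch for a cytopenia that fails to recover is the one that orders discontinuation, so the exception in 6.3 must refer to that branch, and it labels the same event as not requiring discontinuation.

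Two things depend on this. The first is handling. One site may take a subject with an unresolved Grade 4 cytopenia off therapy. Another may keep the subject on hold, because section 6.3 says "Dosing delays to manage drug-related AEs are allowed" and asks for Medical Monitor consultation only before re-initiating after a gap of more than 6 weeks. The second is the count for rule 2. The event counts if the opening of 6.3 is followed to 6.1, and does not count if the exception list is followed. With a threshold of three, one subject classified differently can decide whether enrollment stops.

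**Working it through.** **Reading the sections side by side**

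1. *Section 6.1:* a Grade 3 or Grade 4 cytopenia that does not improve is discontinued.
2. *Section 6.3, opening:* hematologic discontinuation follows 6.1. This agrees with step 1.
3. *Section 6.3, Grade 4 clause:* it applies only to events outside 6.1, 17.1 and 17.2. A cytopenia handled by 6.1 is therefore never within it.
4. *Section 6.3, exception:* it removes from that clause an event the clause never held, and describes it as not requiring discontinuation. This disagrees with steps 1 and 2.
5. *Consequence of the literal reading:* the exception sits under a Grade 4 clause, so an unresolved Grade 3 cytopenia would still be discontinued under 6.1 while an unresolved Grade 4 one would not. That ordering makes no clinical sense and points to a drafting slip.
6. *Redosing:* under 6.1 both drugs stay delayed until the toxicity is below Grade 3. The exception does not change that.
7. *Which events are recorded:* section 6.1 says "Treat autoimmune cytopenias per standard institutional guidelines", and a treated cytopenia is an AE under 11.1.1. For untreated, asymptomatic ones, 11.2.1 says they are not collected, while 11.1.1 also admits values that need further diagnostic tests. The size below concerns recorded events only.

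**Size of the effect on rule 2**

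Inputs from section 12.3: 17 then 16 subjects; interim futility if fewer than 3 CR and fewer than 7 OR; success at 7 or more CR or 17 or more OR of 33; Grade 4+ AE rate 32%; rules 1 and 2 as above. Toxicity is taken as independent of response, rule 3 is left out, and the case is CRR = ORR = 30%, where every response is a CR.

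- Futility stop: F = P(Bin(17, 0.30) ≤ 2) = 0.0774.
- Passing futility and succeeding, before toxicity: E = 0.8674.
- Toxicity stop: T(q) = 1 − P(at most 6 subjects with Grade 4 and at most 2 counted under rule 2), from a trinomial with n = 17 and probabilities q (counted under rule 2), 0.32 − q (other Grade 4) and 0.68 (none).
- Interim stop = 1 − (1 − T)(1 − F). Success = (1 − T) × E.

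*The plan's own figures, rule 1 only (q = 0):* T = 0.2838. Stop = 1 − 0.7162 × 0.9226 = 0.339 (stated: at most 0.34). Success = 0.7162 × 0.8674 = 0.621 (stated: at least 0.62). The same method at CRR 10% and ORR 30% gives stop 0.749 (stated: about 0.75).

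*With rule 2.* The plan gives no rate for rule 2 events, so these are assumptions: other rule 2 events in 2% or 5% of subjects, and refractory recorded Grade 4 cytopenia in a further 1%, 2% or 5%.

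| Other rule 2 events | Cytopenia counted | q | T | Interim stop | Success | Fall in success |
|---|---|---|---|---|---|---|
| 2% | none | 0.02 | 0.2853 | 0.3406 | 0.6200 | – |
| 2% | 1% | 0.03 | 0.2884 | 0.3435 | 0.6172 | 0.003 |
| 2% | 2% | 0.04 | 0.2940 | 0.3487 | 0.6124 | 0.008 |
| 2% | 5% | 0.07 | 0.3291 | 0.3810 | 0.5819 | 0.038 |
| 5% | none | 0.05 | 0.3026 | 0.3565 | 0.6050 | – |
| 5% | 1% | 0.06 | 0.3142 | 0.3673 | 0.5948 | 0.010 |
| 5% | 2% | 0.07 | 0.3291 | 0.3810 | 0.5819 | 0.023 |
| 5% | 5% | 0.10 | 0.3923 | 0.4393 | 0.5272 | 0.078 |

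Interim stopping rises by 0.003 (0.3406 to 0.3435) to 0.083 (0.3565 to 0.4393). Expected subjects affected among 33: 33 × 0.01 = 0.3, 33 × 0.02 = 0.7, 33 × 0.05 = 1.7.

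**The case against.** The best defense is that the bullet meant only that hematologic events are governed by 6.1 and not by the Grade 4 clause. The opening of 6.3 supports this, and so does the scope of the clause. On that view the bullet is redundant, and rule 2, by pointing to 6.3, reaches 6.1 through it. This is probably the intent, and it largely stands: the bullet is better read as a misplaced, self-contradictory exception than as a counter-order to 6.1. What does not stand is that the text says so. The printed list is of events that do not require discontinuation.

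It is also fair that the practical gap is narrow. Section 6.1 sets no time limit for failing to improve, so the moment when a hold becomes a discontinuation already depends on the site, and deleting the bullet does not change that. The allowance to continue a non-offending drug applies on either reading. Rule 1 counts every recorded Grade 4 cytopenia regardless, though only toward 7 of 17.

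A reader might infer two stronger things. One is that 6.3 lets sites redose both drugs through an unresolved Grade 4 cytopenia. It does not, since the delay in 6.1 still applies. The other is that this wording makes the stated 0.62 and 0.34 wrong. Those figures reproduce with no rule 2 events at all. Their omission of rule 2 is a separate matter, and the fall from 0.621 to 0.605 at a 5% rate of other events belongs to it and not to this point.

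**Conclusion.** The inconsistency is real as printed, both between 6.1 and 6.3 and within 6.3. It leaves open whether an unresolved drug-related Grade 4 cytopenia means hold or discontinuation, and whether it counts toward rule 2. An enrollment-stopping safety rule should not depend on that choice.

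The numerical effect of the reading is a fall in success probability of about 0.003 to 0.078. It rests on assumed event rates, on toxicity being independent of response, and on the single case CRR = ORR = 30%. The upper end needs 5% other rule 2 events plus a further 5% refractory cytopenia. The common-event lists in sections 10.1.6 and 10.2.6 name no cytopenia, so the low rates are the more plausible ones, and there the effect is small. Part of the clinical safety summary in section 1.6.2 was not in the text available here, so the true rate remains unknown. The correction is worth making at any rate because it removes a contradiction in a safety instruction at almost no cost.

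**What to change.** - **Section 6.3:** delete the refractory hematologic bullet from the exception list. If a pointer is wanted, put this outside the list: *Hematologic toxicities addressed in section 6.1 are delayed, resumed or discontinued as 6.1 directs.* Deletion affects no other event, because the Grade 4 clause already leaves out what 6.1 addresses.
- **Section 12.3, rule 2:** count Grade 4 AEs requiring discontinuation *as specified in sections 6.1, 6.3, 17.1 and 17.2*. Naming only 6.1 and 6.3 would invite the reading that Grade 4 organ toxicities discontinued under 17.1 or 17.2 are not counted.
- Leave the delay provisions and the non-offending-drug allowances as they are.

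The cost is one bullet and one cross-reference, with no added tests or visits. The downside is that rule 2 becomes slightly easier to reach, by the amounts in the table. When the operating characteristics are next run, a stated rate for rule 2 events would show this directly.
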